### **7.2.6 Sponsor Responsibility for Reporting Adverse Events**

All Serious Adverse Events will be reported to regulatory authorities, IRB/IECs and investigators in Guidelines for Good Clinical Practice.

## **7.3 TRIAL GOVERNANCE AND OVERSIGHT**

### **7.3.1 Stakeholder Group**

This trial was developed in collaboration with a group of stakeholders comprised of Dalhousie University, CIRN, IDRC, Merck and the trial P.I.

### **7.3.2 Trial Steering Committee**

This trial will be conducted in consultation with a Trial Steering Committee. The Trial Steering Committee comprises:

- Sponsor Representatives
- Investigators participating in the trial
- Manufacturer Representative

The Trial Steering Committee will provide guidance on the operational aspects of the trial, and will receive and implement recommendations from the DSMB.

### **7.3.3 Data Safety and Monitoring Board**

To supplement the routine trial monitoring outlined in this protocol, an external DSMB will monitor the interim data from this trial. The voting members of the committee are external to the Sponsor. The members of the DSMB must not be involved with the trial in any other way (e.g., they cannot be trial investigators) and must have no competing interests that could affect their roles with respect to the trial.

The DSMB will make recommendations to the Trial Steering Committee regarding steps to ensure both subject safety and the continued ethical integrity of the trial. Also, the DSMB will review interim safety results, consider the overall risk and benefit to trial participants and recommend to the Trial Steering Committee if the trial should continue in accordance with the protocol. Specific stopping rules can be found in Section 14. Appendix 3.

Specific details regarding composition, responsibilities, and governance, including the roles and responsibilities of the various members and the sponsor protocol team; meeting facilitation; the trial governance structure; and requirements for and proper documentation of DSMB reports, minutes, and recommendations will be described in a separate charter that is reviewed and approved by the DSMB. The DSMB will monitor the trial at an appropriate frequency, as described in the detailed DSMB charter. The DSMB will also make recommendations to the TSC regarding steps to ensure both subject safety and the continued ethical integrity of the trial.

A DSMB recommendation will be communicated to the Sponsor as agreed to in the Collaboration agreement.

## 8.0 STATISTICAL ANALYSIS PLAN

This section outlines the statistical analysis strategy and procedures for the study. If, after the study has begun, but prior to any final database lock, changes are made to primary and/or key secondary hypotheses, or the statistical methods related to those hypotheses, then the protocol will be amended (consistent with ICH Guideline E-9). Changes to exploratory or other non-confirmatory analyses made after the protocol has been finalized, but prior to final database lock, will be documented in a supplemental Statistical Analysis Plan (sSAP) and referenced in the Clinical Study Report (CSR) for the study. Post-hoc exploratory analyses will be clearly identified in the CSR.

### 8.1 Statistical Analysis Plan Summary

Key elements of the statistical analysis plan are summarized below; the comprehensive plan is provided in Sections 8.2.

Study Design Overview	V920 (rVSVΔG-ZEBOV-GP) Ebola Virus Vaccine Candidate in HIV-Infected Adults and Adolescents
Treatment Assignment	Participants in Cohort 1-4, will be randomly assigned to receive one dose of $\geq 2 \times 10^7$ pfu of the study vaccine or the placebo control in a ratio of 4 to 1 (200:50). Participants in Cohort 5 will be randomly assigned to receive one dose of $\geq 2 \times 10^7$ pfu of the study vaccine or the placebo control in a ratio of 4 to 1 (40:10) on Day 0, followed by booster vaccination at Day 56.
Primary Endpoint(s)	Safety, and ZEBOV-specific antibody responses.
Analysis Populations	
The Per-Protocol population (PP) will serve as the primary population for the analysis of immunogenicity data in this study. The Per-Protocol population excludes subjects due to important deviations from the protocol that may substantially affect the results of the primary immunogenicity endpoint(s). For example, subjects who are seropositive at baseline will be excluded from the Per-Protocol population. All subjects who meet the inclusion criteria, were seronegative at baseline, and do not have a major protocol deviation will be included in the per-protocol analysis.
 
The All Subjects as Treated (ASaT) population will be used for the analysis of safety data in this study. The ASaT population consists of all randomized subjects who received at least one dose of study vaccination. Subjects will be included in the treatment group corresponding to the study treatment they actually received for the analysis of safety data using the ASaT population. For most subjects this will be the treatment group to which they are randomized. Subjects who received incorrect study vaccine will be included in the treatment group corresponding to the study vaccine actually received.

Statistical Methods for Immunogenicity Analyses	
Immunogenicity summaries will include: means and 95% CIs of the Geometric Mean Titers (GMT) and Geometric Mean Fold Increase from baseline (GMFI) of ZEBOV-specific antibody responses at baseline and Day 28, Day 84 (Cohort 5 only), Day 180, and Day 365.
 
Immunogenicity summaries will include: counts, percentages, and 95% CIs of subjects who achieve seroconversion (e.g. 4-fold increase) for

	
ZEBOV-specific antibody responses at baseline and Day 28, Day 84 (Cohort 5 only), Day 180, and Day 365.
 
Immunogenicity summaries will include: counts, percentages, and 95% CIs of subjects who achieve seroprotection for ZEBOV-specific antibody responses at baseline and Day 28, Day 84 (Cohort 5 only), Day 180, and Day 365 based on correlate of protection thresholds, if found.
 
Fisher's exact (primary) or Chi-square test (secondary if sample size warrants) will be used to compare the frequency of ZEBOV-specific antibody responses and Student's t (primary) or Wilcoxon rank-sum test (secondary if not normally distributed) will be used to compare ZEBOV-specific GMT ZEBOV-specific antibody between treatment groups. All hypotheses will be evaluated using two-sided tests at <math>\alpha = 0.05</math>. Superiority of immune response will be defined as a statistically significant difference.

Statistical Methods for Safety Analyses	
Counts and percentages of solicited local and systemic reaction frequency and severity among study cohorts (various CD4 counts and ages) will be summarized.
 
Fisher's exact or Chi-square test will be used to compare the frequency of local and systemic reactions between treatment groups as specified in the SAP.

Multiplicity	Adjustment for multiplicity will not be performed.
Sample Size and Power	
For immunogenicity assessment, there is 80% power to detect a Geometric Mean Ratio (GMR) of 1.6 (V920 GP-ELISA GMT of 58 EU/mL vs. Placebo GP-ELISA GMT of 36 EU/mL, the lower limit of quantification [LLOQ]) and 90% power to detect a GMR of 1.7 (V920 GP-ELISA GMT of 62 EU/mL) if comparing all five cohorts (N=200 V920 vs. N=50 Placebo) combined. This power analysis assumes a 10% dropout, a standard deviation of 1 on the log scale, and a 2-sided 5%.
 
There is 80% power to detect a GMR of 2.9 (V920 GP-ELISA GMT of 105 EU/mL) and 90% power to detect a GMR of 3.4 (V920 GP-ELISA GMT of 124 EU/mL) if comparing each cohort independently (N=40 V920 vs. N=10 Placebo). This power analysis assumes a 10% dropout, a standard deviation of 1 on the log scale, and a 2-sided 5%.
 
For safety assessment, there is 80% power to detect a 12% difference in event rates that occur with a frequency of 1% in the control group if comparing all four cohorts (N=200 V920 vs. N=50 Placebo) combined and a 46% difference if comparing each cohort independently (N=40 V920 vs. N=10 Placebo).

Subgroup Analyses and Effect of Baseline Factors	Safety, immunogenicity, seroprotection, and seroconversion will be summarized for these pre-specified subgroups: CD4 cell count ( $\geq 500$ cells/mm $^3$ , $> 350$ and $< 500$ cells/mm $^3$ , $CD4 \geq 200$ and $\leq 350$ cells/mm $^3$ ), and age (adults, adolescents).
Interim Analyses	Four safety analyses will be conducted, one for each of the first four cohorts, when each cohort will have completed 42 days of follow-up post-vaccination

## 8.2 Statistical Analysis Plan Detailed Description

### 8.2.1 Responsibility for Analyses/In-House Blinding

The statistical analysis of the data obtained from this study will be the responsibility of the CIRN Biostatistics department.

### 8.2.2 Objectives/Hypotheses

(1) Objective: Evaluate the safety and tolerability of V920 in HIV-infected adults and adolescents.

(2) Objective: Evaluate the immunogenicity of V920 via ZEBOV-specific antibody responses induced by V920 at D28 in HIV-infected adults and adolescents.

Primary Hypotheses:

- 1) The geometric mean titer (GMT) of GP-ELISA in V920 vaccinated HIV-infected adults and adolescents will be superior to the GMT of the GP-ELISA in placebo vaccinated HIV-infected adults at Day 28 in Cohorts 1-5 combined.

### 8.2.3 Analysis Endpoints

#### 8.2.3.1 Immunogenicity Endpoints

The V920 vaccine candidate is a live recombinant vesicular stomatitis virus (VSV) expressing the glycoprotein (GP) of Zaire Ebola virus (ZEBOV). Two independent serological and molecular assays are currently being developed to clinically evaluate the immunogenicity of V920:

- GP-ELISA measures the total IgG antibody response and can also be correlated to the plaque reduction neutralization assay (PRNT) titer result.
- Plaque reduction neutralization assay (PRNT) is a functional assay for quantitating the neutralizing antibody response elicited by the vaccine.

Participants who consent to bio-bank will undergo up to four blood draws in cohorts 1-4: at baseline on the day of vaccination before vaccine or placebo is administered; at D28 post-vaccination; at D180 post-vaccination; and at D365 post-vaccination.

### 8.2.4 Analysis Populations

#### 8.2.4.1 Immunogenicity Analysis Populations

The Per-Protocol population (PP) will serve as the primary population for the analysis of immunogenicity data in this study. The Per-Protocol population excludes subjects due to important deviations from the protocol that may substantially affect the results of the primary

immunogenicity endpoint(s). For example, subjects who are seropositive at baseline will be excluded from the Per-Protocol population. All subjects who meet the inclusion criteria, were seronegative at baseline, and do not have a major protocol deviation will be included in the per-protocol analysis.

The final determination of subjects with major protocol deviations, and thereby the composition of the Per- Protocol population, will be made prior to the unblinding of the database for the primary CSR (see Section 8.2.1) and will be documented in a separate memo.

A supportive analysis using the Full Analysis Set (FAS) population may be performed. The FAS population consists of all randomized subjects with serology data.

#### 8.2.4.2 Safety Analysis Populations

The All Subjects as Treated (ASaT) population will be used for the analysis of safety data in this study. The ASaT population consists of all randomized subjects who received at least one dose of study vaccination. Subjects will be included in the treatment group corresponding to the study treatment they actually received for the analysis of safety data using the ASaT population. For most subjects this will be the treatment group to which they are randomized. Subjects who received incorrect study vaccine will be included in the treatment group corresponding to the study vaccine actually received.

Details on the approach to handling missing data for safety analyses are provided in Section 8.2.5 Statistical Methods.

### 8.2.5 Statistical Methods

#### 8.2.5.1 Statistical Methods for Immunogenicity Analyses

Immunogenicity summaries will include: means and 95% CIs of the Geometric Mean Titers (GMT) and Geometric Mean Fold Increase from baseline (GMFI) of ZEBOV-specific antibody responses at baseline and Day 28, Day 84 (Cohort 5 only), Day 180, and Day 365.

Immunogenicity summaries will include: counts, percentages, and 95% CIs of subjects who achieve seroconversion (e.g. 4-fold increase) for ZEBOV-specific antibody responses at baseline and Day 28, Day 84 (Cohort 5 only), Day 180, and Day 365.

Immunogenicity summaries will include: counts, percentages, and 95% CIs of subjects who achieve seroprotection for ZEBOV-specific antibody responses at baseline and Day 28, Day 84 (Cohort 5 only), Day 180, and Day 365 based on correlate of protection thresholds, if found. Fisher's exact (primary) or Chi-square test (secondary if proportion size warrants) will be used to compare the frequency of ZEBOV-specific antibody responses and Student's t (primary) or Wilcoxon rank-sum test (secondary if not normally distributed) will be used to compare ZEBOV-specific GMT ZEBOV-specific antibody between treatment groups. All hypotheses will be evaluated using two-sided tests at  $\alpha = 0.05$ . Superiority of immune response will be defined as a statistically significant difference.

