HIV RNA (reservoirs) (~20 mls combined with HIV DNA and HIV TILDA below)		x				x		x	x	
HIV DNA (reservoirs) (see volume above)		x				x		x	x	
HIV TILDA (reservoirs) (see volume above)		x				x		x	x	
*Biobank samples-optional (~35mls)		xb				x		x	x	
Total Blood volumes (*including optional Biobank sample)	~ 40mls	~64mls (*~89mls)	~29mls	~29mls	~29mls	~69mls (*~94mls)	~29mls	~52mls (*~87mls)	~52mls (*~87mls)	
a. Specimens should be obtained for rVSV detection by PCR in through 42 days from skin vesicles, joint fluid, or skin biopsies b. Specimens should be obtained before vaccination										

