### 8.2.7 Sample Size and Power Calculations

For immunogenicity assessment, there is 80% power to detect a Geometric Mean Ratio (GMR) of 1.6 (V920 GP-ELISA GMT of 58 EU/mL vs. Placebo GP-ELISA GMT of 36 EU/mL, the lower limit of quantification [LLOQ]) and 90% power to detect a GMR of 1.7 (V920 GP-ELISA GMT of 62 EU/mL) if comparing all five cohorts (N=200 V920 vs. N=50 Placebo) combined. This power analysis assumes a 10% dropout, a standard deviation of 1 on the log scale, and a 2-sided 5%.

There is 80% power to detect a GMR of 2.9 (V920 GP-ELISA GMT of 105 EU/mL) and 90% power to detect a GMR of 3.4 (V920 GP-ELISA GMT of 124 EU/mL) if comparing each cohort independently (N=40 V920 vs. N=10 Placebo). This power analysis assumes a 10% dropout, a standard deviation of 1 on the log scale, and a 2-sided 5%.

For safety assessment, there is 80% power to detect a 12% difference in event rates that occur with a frequency of 1% in the control group if comparing four cohorts (N=200 V920 vs. N=50 Placebo) combined and a 46% difference if comparing each cohort independently (N=40 V920 vs. N=10 Placebo).

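### The GMT comparison does not use the pre-vaccination titre as a covariate, which may cost some precision: probably little in the Per-Protocol set, more in the FAS

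*Combined protocol and SAP*

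**What the plan says.** Both flow charts in section 6.0 schedule ZEBOV binding and neutralising antibodies at Day 0, with a footnote: "Specimens should be obtained before vaccination". Sections 8.1 and 8.2.5.1 then compare GMTs between arms by a two-sample test with no covariate: "Student's t (primary) or Wilcoxon rank-sum test (secondary if not normally distributed) will be used to compare" them. On the error rate, "All hypotheses will be evaluated using two-sided tests at" 0.05.

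Baseline titre is used in three other places: the descriptive fold increase (GMFI), seroconversion (for example a 4-fold rise), and Per-Protocol membership, because section 8.2.4.1 removes subjects seropositive at baseline. The same section makes Per-Protocol the primary immunogenicity population. The FAS (all randomised subjects with serology data) is supportive and optional.

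Section 8.2.7 gives power for the pooled comparison, "if comparing all five cohorts (N=200 V920 vs. N=50 Placebo) combined". It states that "there is 80% power to detect a Geometric Mean Ratio (GMR) of 1.6", with "90% power to detect a GMR of 1.7 (V920 GP-ELISA GMT of 62 EU/mL"). The comparator is a "Placebo GP-ELISA GMT of 36 EU/mL, the lower limit of quantification [LLOQ"]. The inputs are: "This power analysis assumes a 10% dropout, a standard deviation of 1 on the log scale, and a 2-sided 5"%.

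The documents state no correlation between baseline and post-vaccination titre, and no titre that defines seronegative.

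**The concern.** In a randomised comparison of log titres, a pre-treatment measurement of the same quantity is an obvious covariate. Where it predicts the outcome, adjustment narrows the interval for the GMT ratio and raises power, with no new data. The trial pays for the Day 0 sample in all five cohorts but leaves it out of the between-arm GMT test at Days 28, 84, 180 and 365.

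Precision is scarcest in the single-cohort comparisons of 40 v 10, which include the Cohort 5 hypothesis 28 days after dose 2 (section 3.1). At stake is the width of the interval for the GMT ratio and some power. The validity of the test is not in question.

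**Working it through.** **Inputs from section 8.2.7.** SD 1 on the log scale; 10% dropout, so 200 v 50 becomes 180 v 45 and 40 v 10 becomes 36 v 9; two-sided 5%; placebo GMT 36 EU/mL, equal to the LLOQ. **Assumed here:** the correlation rho between baseline and Day 28 log titre, the seronegative cut-off, and the baseline distribution.

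**1. The plan's own power.** The standard error of the log GMT ratio is SD × sqrt(1/n1 + 1/n0); power follows from the noncentral t distribution.

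- Combined: sqrt(1/180 + 1/45) = 0.1667. ln 1.6 = 0.470, and 0.470/0.1667 = 2.82; with 223 df, power is 80.2%. At 62/36 = 1.722 it is 90.1%.
- One cohort: sqrt(1/36 + 1/9) = 0.3727. ln 2.9 = 1.065, and 1.065/0.3727 = 2.86; with 43 df, power is 79.7%. At 124/36 = 3.444 it is 90.0%.

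The stated figures reproduce with natural logs. An SD of 1 on the log10 scale does not reproduce them (23% power).

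**2. Effect of adjustment.** Residual SD = sqrt(1 − rho²), with one df fewer. Here rho is the correlation that remains in the analysed set, in both arms.

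| rho remaining | variance removed | power, 180 v 45, GMR 1.6 | power, 36 v 9, GMR 2.9 |
|---|---|---|---|
| 0 | 0% | 80.2% | 79.7% |
| 0.2 | 4% | 81.8% | 81.3% |
| 0.3 | 9% | 83.7% | 83.3% |
| 0.5 | 25% | 90.0% | 89.7% |

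**3. What remains in the Per-Protocol set.** Simulated with baseline log SD 1, baseline median 18 to 60 EU/mL, sub-LLOQ values set to 36, and subjects above the cut-off removed.

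- Cut-off at the LLOQ (36): recorded baseline is constant, so rho is 0 and the gain is nil.
- Cut-off 72 to 200: an underlying rho of 0.3 falls to about 0.15–0.23 (2–5% of variance); 0.5 falls to about 0.25–0.39 (6–15%).

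By the formula in step 2, 2% gives 81.0% power and 15% gives 86.1%, against 80.2%. The interval on the log scale narrows by 1 − sqrt(0.98) = 1% to 1 − sqrt(0.85) = 8%.

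**4. Is a cut-off at the LLOQ implied?** Taken literally, an untreated GMT of 36 with log SD 1 puts half of unvaccinated subjects above 36. A cut-off there would remove half the sample, while the plan allows for a 10% loss. A cut-off that removes 10% would be 36 × exp(1.28) = about 130 EU/mL. At that cut-off and a median of 36, about 4–5% of variance is removed for an underlying rho of 0.3 and 12–14% for 0.5.

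**5. FAS.** With no exclusion, the only shrinkage comes from censoring at the LLOQ. For an underlying rho of 0.5 and a median of 36, about 18–20% of variance is removed (12–23% for medians of 18 to 60). The interval narrows by 1 − sqrt(0.80) = 11% at 20%.

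**6. Cost if baseline is uninformative.** The lost df alone changes almost nothing. Adding the variance from chance baseline imbalance, simulated power at 36 v 9 falls from 79.8% to 78.7%, about 1 point. At 180 v 45 the loss is negligible.

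**The case against.** The strongest case against is that the primary population largely removes the covariate. Seropositive subjects leave the Per-Protocol set, prior filovirus infection and filovirus vaccine-trial participation are entry exclusions (5.1.3), and the power calculation puts untreated titres at the assay floor. This stands as a reason to expect a small gain. It does not establish a zero gain, because that needs a seronegative cut-off at the LLOQ, which the documents do not state.

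The SD of 1 is a working input and not evidence that baseline predicts Day 28, least of all in vaccinees, whose titre mainly reflects vaccine response. This also stands. With 4:1 allocation the pooled slope is driven by the V920 arm: if rho is 0.5 in placebo and 0 in V920, variance falls by only about 6% and power reaches only about 81%.

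The benefit may not affect any decision. Section 4.1.3 reports 100% seroconversion by Day 28 in Phase 1, and at an assumed GMR of 4 the unadjusted test already has over 99.9% power at 180 v 45 and 95% at 36 v 9. The gain is then mainly in the precision of the estimate. Section 4.2.2.2 does allow that HIV-infected subjects may respond less.

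Finally, setting sub-LLOQ values to one number can make the covariate constant, so that its coefficient cannot be estimated. This is correct, and the plan would need a stated fallback.

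**Conclusion.** The point holds as a minor, conditional one. The unadjusted t-test may give up some precision. In the Per-Protocol set the likely loss is about 2–15% of variance, assuming an underlying rho of 0.3 to 0.5 in both arms and a cut-off above the LLOQ; it is nil if all recorded baselines equal the LLOQ. The case is clearest for the FAS, at about 20% for an assumed rho of 0.5.

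A reader might infer that the plan forgoes a rise from 80% to 90% power in its primary analysis. The documents do not support that: it needs a correlation of 0.5 to remain in both arms after seropositives are removed, and they supply no correlation at all. Nor do they support reading the t-test as biased or invalid, or baseline as used only for GMFI. Confidence in the size of the gain is low.

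**What to change.** In sections 8.1 and 8.2.5.1, specify an ANCOVA of log titre on treatment with log Day 0 titre as covariate and sub-LLOQ values set to one fixed value. Report the adjusted GMT ratio with its 95% CI. Apply it at Day 28, at Day 84 in Cohort 5, at Days 180 and 365, and in any FAS analysis. Name Day 0 explicitly: the Cohort 5 sample before dose 2 is post-randomisation and should not serve as the covariate.

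State that the model reduces to the t-test if recorded baseline is constant, and keep the unadjusted test as a sensitivity analysis.

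Cost: SAP wording and one degree of freedom, with no new samples or visits. The downside is about 1 point of power in a 36 v 9 comparison if baseline is uninformative. Because this changes the method for a primary hypothesis, section 8.0 requires a protocol amendment before final database lock.

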The study will enroll approximately 250 participants, ~100 at 2 sites in Canada and ~150 at 2 sites in Africa. Depending on recruitment rates, participants may be reallocated between sites in order to ensure the integrity of the study. Overall ~200 participants will receive the study vaccine and ~50 will receive placebo. Sequential enrollment of five study Cohorts will occur over time at each study site according to CD4 T-cell counts: Cohort 1 will include adult subjects with  $CD4 \geq 500 \text{ cells/mm}^3$ , Cohort 2  $CD4 > 350$  and  $< 500 \text{ cells/mm}^3$ , Cohort 3  $CD4 \geq 200$  and  $\leq 350 \text{ cells/mm}^3$ , Cohort 4 adolescents  $CD4 \geq 200 \text{ cells/mm}^3$ , and Cohort 5 adults and adolescents with  $CD4 \geq 200 \text{ cells/mm}^3$  receiving two doses 56 days apart. Enrollment and vaccine administration will begin with the cohort with the highest CD4 count. When the D42 post-vaccination period is completed for all subjects in Cohort 1, and the Data Safety Monitoring Board (DSMB) has reviewed the safety data and determined that there are no concerns, enrollment and vaccination of the next CD4 cohort may begin. Similarly, when the D42 safety data for Cohort 2 has been reviewed/approved by the DSMB, enrollment and vaccination of participants in Cohort 3 may begin. Cohort 4 with adolescents 13-17 years of age (inclusive) with  $CD4 \geq 200$  will be enrolled after D42 safety is reviewed in adults with  $CD4 \geq 200$ . Within each Cohort 1-4, participants will be randomly assigned to receive one dose of  $\geq 2 \times 10^7 \text{ pfu}$  of the study vaccine or the placebo in a ratio of 4 to 1. In Cohort 5, participants will be randomly assigned to receive one dose of  $\geq 2 \times 10^7 \text{ pfu}$  of the study vaccine or the placebo in a ratio of 4 to 1, and followed by a matching vaccine or placebo dose at Day 56. All participants will complete memory aids for 42 days following each vaccination.

Specific procedures to be performed during the trial, as well as their prescribed times and associated visit windows, are outlined in the Trial Flow Chart - Section 6.0. Details of each procedure are provided in Section 7.0 – Trial Procedures.

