### **5.4 Stratification**

To satisfy the requirement that each site enrolls at least one placebo subject in each cohort, enrollment will proceed until treatments have been randomized to at least one complete block of subjects (consisting of four subjects receiving treatment and one receiving placebo) at each site.

Treatment allocation/randomization will be stratified by the 5 cohort groups:

- Cohort 1: Screening CD4 cell counts for adults: CD4 cells/mm^3  $\geq 500$
- Cohort 2: Screening CD4 cell counts for adults: CD4 cells/mm^3  $>350$  and  $< 500$
- Cohort 3: Screening CD4 cell counts for adults: CD4 cells/mm^3  $\geq 200$  and  $\leq 350$
- Cohort 4: Screening CD4 cell counts for adolescents, age 13 to 17: CD4 cells/mm^3  $\geq 200$
- Cohort 5: Screening CD4 cell counts for adults and adolescents, age 13 to 17: CD4 cells/mm^3  $\geq 200$  with 2 doses.

All sites are stratified by site (two sites per cohort).

Cohort 5 is stratified by site, and by age group (adolescent vs. adult). Once three blocks of five adolescents have been enrolled, with at least one block at each site, the requirement to enroll at least 12 adolescents in Cohort 5 will be met.

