### 8.2.5.2 Statistical Methods for Safety Analyses

Safety parameters will be compared between V920 and placebo control. Fisher's exact or Chi-square test will be used to compare the frequency of local and systemic reactions between treatment groups as specified in the SAP.

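### Randomisation is stratified by cohort, site and (in Cohort 5) age group, but the pooled comparisons use unstratified tests: this loses precision without causing bias, and is nearly free to recover.

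*Combined protocol and SAP*

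**What the plan says.** **Design.** Section 5.4 states that "Treatment allocation/randomization will be stratified by the 5 cohort groups" and adds "All sites are stratified by site (two sites per cohort"). For the last cohort, "Cohort 5 is stratified by site, and by age group (adolescent vs. adult"). A block is described as "consisting of four subjects receiving treatment and one receiving placebo".

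**Primary comparison.** The first primary hypothesis (Sections 3.1 and 8.2.2) pools everyone: V920 recipients against "placebo vaccinated HIV-infected adults at Day 28 in Cohorts 1-5 combined".

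**Tests.** Under Section 8.2.5.1, Student's t (primary) or Wilcoxon rank-sum "will be used to compare ZEBOV-specific GMT ZEBOV-specific antibody between treatment groups"; antibody response frequency is compared by Fisher's exact or chi-square. For safety, Section 8.2.5.2 says "Fisher's exact or Chi-square test will be used to compare the frequency of local and systemic reactions between treatment groups". Section 8.1 repeats these methods.

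**What is absent.** No test in Section 8 has a cohort, site or age term. CD4 group and age group appear only as descriptive subgroup summaries (8.2.8), and site appears in no analysis. Cochran-Mantel-Haenszel is in the abbreviation list but is never applied. Section 8.2.5.2 defers to the SAP for detail; Section 8 is that SAP and gives none.

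**The concern.** The cohorts differ by design in factors that plausibly drive response and reactogenicity: CD4 count, age and, through site, region. They also enrol one after another, so a cohort term would absorb calendar time as well. Blocking holds the arms at 4:1 within each stratum, so the true sampling variance of the arm difference contains only within-stratum variance. An unstratified test estimates that variance from the total spread. Its standard error is therefore too large to the extent that the strata predict outcome, and the protection bought by stratifying is not used.

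At stake are the width of the between-arm interval and some power. This matters most for safety, which is the first primary objective and has only about 50 placebo recipients, and for Cohort 5, with 9 evaluable placebo recipients after the planned dropout.

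**Working it through.** **Inputs (Section 8.2.7).** 200 v 50 pooled and 40 v 10 per cohort; 10% dropout, giving 180 v 45 and 36 v 9; SD 1 on the natural-log scale; two-sided 5%; 80% power claimed at GMR 1.6 pooled and GMR 2.9 per cohort.

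**1. Reproduce the plan's figure.** SE = 1 × sqrt(1/180 + 1/45) = 0.1667. ln 1.6 / SE = 0.470/0.1667 = 2.82. With a critical t of 1.971, power ≈ Φ(2.82 − 1.971) = Φ(0.849) ≈ 80.2%. At 36 v 9 and GMR 2.9 the t calculation gives 79.8%. The stated power is that of the unadjusted test.

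**2. Let the strata explain a share R² of log-titre variance.** R² is an assumption. With 4:1 in every stratum the true SE is 0.1667 × sqrt(1 − R²), while the t-test still estimates 0.1667.

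- Unadjusted power = Φ[(2.82 − 1.971)/sqrt(1 − R²)]; type I error = 2Φ[−1.971/sqrt(1 − R²)].
- Adjusted power = Φ[2.82/sqrt(1 − R²) − 1.971]; relative interval width = sqrt(1 − R²). The 11 degrees of freedom for 12 strata barely matter (212 against 223).

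Example at R² = 20%, sqrt(0.8) = 0.894: unadjusted Φ(0.849/0.894) = 82.9%; adjusted Φ(3.153 − 1.971) = 88.1%.

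| R² | Unadjusted power | Adjusted power | Gain (points) | Relative width | Type I error, unadjusted |
|---|---|---|---|---|---|
| 0 | 80.2% | 80.2% | 0 | 1.00 | about 5% |
| 5% | 80.8% | 82.1% | 1.3 | 0.975 | 4.3% |
| 10% | 81.5% | 84.1% | 2.6 | 0.949 | 3.8% |
| 20% | 82.9% | 88.1% | 5.2 | 0.895 | 2.8% |
| 30% | 84.5% | 91.9% | 7.4 | 0.837 | 1.85% |

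Simulated stratified blocks with 10% dropout (20,000 runs) agree. At R² = 20%, power was 82.2% v 87.4%, log-scale interval width 0.657 v 0.589, and type I error 2.8% v 4.8%. At R² = 0, power was 80.5% v 80.2%.

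**3. Cohort 5 alone (36 v 9, GMR 2.9, 3 extra degrees of freedom).** Unadjusted v adjusted: 80.0% v 79.6% at R² = 0, 81.2% v 83.6% at 10%, 84.2% v 91.5% at 30%.

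**4. Flat placebo arm.** Section 8.2.7 puts the placebo GMT at the lower limit of quantification (LLOQ), and the per-protocol set excludes baseline seropositives (8.2.4.1). Stratum effects may then sit mainly in the vaccine arm. A simulation with placebo SD 0.3 (assumed, no stratum effect) and vaccine SD 1 gave power at GMR 1.6 of 97.8% v 98.5% (R² = 10%) and 98.8% v 99.7% (R² = 30%), with intervals about 4% to 12% narrower.

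**5. Safety, Fisher v Mantel-Haenszel test over 12 strata (200 v 50, 4,000 runs).**

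| Event rates, placebo v V920 | No stratum effect | Stratum logit SD 1 (assumed) |
|---|---|---|
| 1% v 13% (8.2.7) | 83.2% v 87.1% | 89.2% v 93.1% |
| 20% v 40% (assumed) | 75.9% v 77.9% | 62.9% v 72.6% |

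Part of this gain is Fisher's discreteness, since it appears with no stratum effect. For scale, at an assumed 10% event rate in both arms the unstratified 95% half-width on the risk difference is 1.96 × sqrt[0.09 × (1/200 + 1/50)] = 0.093, about ±9 points.

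**6. Which strata?** Two sites per cohort gives 4×2 + 2×2 = 12 strata. But Section 2.1 says "Sequential enrollment of five study Cohorts will occur over time at each study site", and it lists four sites. That would give 4×4 + 4×2 = 24 strata, averaging 50/8 = 6.25 subjects and 1.25 placebo recipients each in Cohort 5.

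**The case against.** The planned tests are valid. With 4:1 blocks they err on the conservative side, and the claimed 80% power is met or exceeded. No R² can be taken from the documents. With placebo titres near the LLOQ, the equal-variance picture in steps 1 and 2 fits poorly, and step 4 shows a power gain of about one point. Section 4.1.3 reports 100% seroconversion in Phase 1; at a GMR of about 4 (the four-fold rise that 8.2.5.1 gives as an example), both analyses have essentially 100% power pooled. The plan also specifies 95% CIs for GMTs, fold rises and percentages but none explicitly for the between-arm ratio, so the wider interval is the one implied by the t-test.

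All of this stands, and it limits the size of the point. It does not remove it: adjustment costs almost nothing when the strata are uninformative and helps when they are not. The unequal-variance argument is a reason for a robust standard error, which the fix includes.

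Stronger readings that the documents do not support:

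- A reader might set adjusted power of 84% to 92% against the stated 80% and infer a gain of 4 to 12 points. That compares two different situations; when strata matter, the t-test's own power rises too.
- A reader might see a second contradiction in three adolescent blocks covering every site. With two sites per cohort three blocks suffice, so this only restates the conflict between 5.4 and 2.1.
- A reader might infer that CD4 group is confounded with region. That depends on which sites enrol each cohort, which the text leaves open, and it would affect only the descriptive subgroup summaries, not the randomised comparison.

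**Conclusion.** The point holds as lost efficiency, not bias and not a false-positive risk. For R² of 10% to 30% the GMR interval would be about 5% to 16% narrower and power at GMR 1.6 about 3 to 7 points higher. Under the flat-placebo assumption the interval gain is nearer 4% to 12%. At R² = 0 there is no gain. The direction follows from the design; the size rests on an R² with no source in the documents. The pooled superiority conclusion is very unlikely to depend on it. The benefit lies in a tighter effect estimate, in safety and in Cohort 5.

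Two neighbouring matters are separate from the ignored strata: Section 8.2.5.2 names no interval on any safety difference, and Sections 5.4 and 2.1 disagree on sites per cohort. The second must be settled before the strata can be coded.

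**What to change.** - **GMT (primary):** linear model of log titre on arm, cohort, site and, for Cohort 5, age group, with a heteroscedasticity-robust standard error (small-sample corrected for Cohort 5). Report the adjusted GMR with 95% CI. Keep the t-test as supportive.
- **Response frequency and safety:** Mantel-Haenszel risk difference stratified by cohort, with 95% CI, alongside the exact p-value. State which governs if the two disagree, and name an interval method that still works when one arm has 0% or 100%.
- **Sparse strata:** state before unblinding when sites collapse to region (Canada, Africa), for example a minimum placebo count per stratum.
- **Separately:** reconcile Section 5.4 with Section 2.1 on which sites enrol each cohort, and list the resulting strata.

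**Cost.** No new data, since every factor is recorded at randomisation, and minor programming. Section 8.0 requires a protocol amendment when methods for primary hypotheses change, so the GMT change needs one before database lock.
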